9.2 Antiemetics

Antiemetics may be used at the discretion of the attending physician.

9.3 Blood Products

Blood products are permissible.

9.4 Neulasta and Neupogen

Neulasta and Neupogen should not be started as part of initial therapy and are not usually necessary with TAS102 but may be used.

9.5 Diarrhea

Diarrhea should be managed with loperamide. The recommended dose of loperamide is 4 mg at first onset, followed by 2 mg every 2-4 hours until diarrhea free (maximum 16 mg/day). Use of alternative agents such as Lomotil and tincture of opium is permissible.

10.0 ADVERSE EVENT (AE) REPORTING AND MONITORING

10.1 Adverse Event Characteristics

CTCAE term (AE description) and grade: The descriptions and grading scales found in the revised NCI Common Terminology Criteria for Adverse Events (CTCAE) version 5.0 will be utilized for AE reporting. All appropriate treatment areas should have access to a copy of the CTCAE version 5.0.

Adverse event monitoring and reporting is a routine part of every clinical trial. First, identify and grade the severity of the event using the CTCAE v5.0. Next, determine whether the event is expected or unexpected and if the adverse event is related to the medical treatment or procedure. With this information, determine whether the adverse event must be reported as an expedited report.

The safety reporting period begins after the subject has signed the informed consent and ends 28 days after the last dose of study drug. It is only required that SAEs be reported following consent and prior to radiation therapy initiation, while all AEs (serious and non-serious) be reported thereafter.

10.2 Expected vs. Unexpected

The determination of whether an AE is expected is based on the agent-specific information provided in this protocol. Unexpected AEs are those not listed in the agent-specific information provided in this protocol.

Note: "Unexpected adverse experiences" means any adverse experience that is neither identified in nature, severity, or frequency of risk in the information provided for IRB review nor mentioned in the consent form.

10.3 Reporting Clinical Safety Data to Taiho

For the purposes of this Agreement an Adverse Event (AE) shall mean any untoward medical occurrence whether thought to have been caused by the study drug(s) or the Clinical Trial procedures or not and Serious Adverse Event (SAE) shall mean any adverse event which is fatal, life threatening, disabling or Incapacitating, requires in-patient hospitalization or prolongs existing hospitalization, Is a congenital anomaly In the off-spring of the patient or which may require Intervention to prevent the previously stated outcomes.

For the purposes of this Clinical Trial, other experiences with the TAIHO Investigational Medicinal Product(s) IMP shown below should also be reported to TAIHO:

- A. Drug exposure during pregnancy and lactation, or paternal drug exposure
- B. Experience In patients below 18 years of age (depending on Inclusion criteria)
- C. Lack of drug effect
- D. Unintended beneficial effect

- E. Any suspected transmission of an infectious agent by a medicinal product
- F. Product quality complaints associated with possible safety issue(s)
- G. Drug or food interaction
- H. Overdose
- I. Medication error
- J. Misuse
- K. Occupational exposure

10.3.1 Reporting Clinical Safety Information to TAIHO Oncology

- a. The Principal Investigator shall monitor the Clinical Trial Subject for adverse events and fulfil all the reporting requirements to FDA in accordance with Applicable Laws. The Principal Investigator shall also inform Taiho Oncology of serious adverse events:
 - Unexpected Fatal or Life Threatening Suspected Adverse Reactions- Report to Taiho Oncology within 24 hours
 - Serious & Unexpected Suspected Adverse Reactions- Report to Taiho Oncology within 24 hours.
 - All other Serious cases (Expected and Related; Expected and Not related; Unexpected and Not related)- Report to Taiho Oncology within 2 weeks of awareness.
- All serious adverse events are to be reported via a MedWatch Form and are to be sent to the Taiho Oncology, via [contact] or e-mail: [contact] (please note the underscore between '102' and 'Safety').
- c. MedWatch reports must clearly specify SAE term(s) and corresponding Principal Investigator causality assessment.
- d. Taiho Oncology will send SUSARs to Regulatory Authorities via a MedWatch form within 7 Calendar Days for all fatal/life threatening events and 15 Calendar Days for all other serious events.

10.3.2 Drug Exposure During Pregnancy and Lactation, or Paternal Drug Exposure Reports

The Institution will report Exposure During Pregnancy and Lactation, or Paternal Drug Exposure on any Clinical Trial Subject while participating in the Clinical Trial, and following exposure to a TAIHO IMP, to TAIHO (as specified below) using copies of the original Pregnancy Report Form and within two weeks of first becoming aware of the pregnancy or exposure. If the partner of a Clinical Trial Subject becomes pregnant, the Institution may collect information about the pregnancy and birth if the partner agrees.

The Clinical Trial Subject will also be followed by the Institution to determine the outcome of the pregnancy (including any premature termination of the pregnancy). Information on the status of the mother and child will be forwarded to TAIHO. The Institution must provide final outcome of pregnancy to TAIHO. If any SAE(s) is observed in Clinical Trail Subject or fetus/child, then SAE(s) must also be reported to TAIHO following SAE Reporting guidelines.

Routing of Drug Exposure During Pregnancy and Lactation, or Paternal Drug Exposure Reports

Such reports and Information as outlined above, Including Investigator causality assessments against all concerned TAIHO IMP(s) and English translations where reporting Is from a non-English speaking country, shall be sent:

- by facsimile to PV CONTACT NUMBER :[contact] OR
- by e-mail to: [contact] (please note the underscore between '102' and 'Safety')

Requesting Follow up information:

The institution will provide TAIHO with details of whom TAIHO shall address requests for follow up Information on SAE and pregnancy cases reported from this Clinical Trial, and further agree to update such contact details as necessary. At the time of this Agreement, all such requests should be addressed to: [name]

SAE Reconciliation

Reconciliation shall be performed quarterly as an exchange of Line Listings or other means in English. On a quarterly basis, the institution shall provide to TAIHO a line listing or other means of cumulative SAE received to date. At the end of the Clinical Trial a global reconciliation shall be performed. Please reference contact information when sending this reconciliation. All serious adverse events via a MedWatch Form need to be sent to the FDA and to Taiho Oncology, Inc., via [contact] or e-mail: [contact] (please note the underscore between '102' and 'Safety').

DSUR

If requested by Institution, TAIHO shall provide the Institution with the final version of this DSUR report within 15 calendar days after submission to health agencies and ethics committees.

11.0 TREATMENT EVALUATION

11.1 Guidance for radiological tumor evaluation

Repeat non-contrast pelvic MRI to rule out progressive disease and ensure surgical resectability is required as per standard of care recommendations (22). Pelvic MRI should be booked within 56 days of completion of cycle #6 of TASOX, ie within 1-56 days AFTER day #14, cycle 6. Radiographic tumor staging should be performed and reported per the initial, staging MRI. See APPENDIX I for guidance.

11.2 Pathological Tumor Response

Pathology reports for the TME resection must be submitted de-identified reports via email to tas-[contact].

11.3 Definition of Surgical Margin Status

Margins to be considered are:

- Proximal Margins
- Distal Margins
- Radial Margins, synonymously termed circumferential margin.

Margin Positivity: A surgical margin is POSITIVE if the pathologist notes tumor within ≤ 1 mm of any edge of the primary tumor specimen.

A surgical margin is NEGATIVE if the pathologist notes that there is NO tumor within > 1mm of any edge of the primary tumor specimen.

11.4 Definition of pathologic stage

Derivation of the Neoadjuvant response (NAR) score requires pathologic staging information from the TME resection specimen staged according to the AJCC8th edition schema:

T describes how far the main (primary) tumor has grown into the wall of the intestine and whether it has grown into nearby areas. Because this information will be ascertained from the surgical pathology report it is denoted with a prefix "p". Because it is ascertained after neoadjuvant treatment, the prefix "y" is also added (e.g., ypT3).

Tx Primary tumor cannot be assessed

- T0 No evidence of primary tumor
- Tis Carcinoma in situ: intraepithelial or invasion of lamina propria
- T1 Tumor invades submucosa
- T2 Tumor invades muscularis propria
- T3 Tumor invades through the muscularis propria into pericolorectal tissues
- T4a Tumor penetrates to the surface of the visceral peritoneum

T4b Tumor directly invades or is adherent to other organs or structures

N describes the extent of spread to nearby (regional) lymph nodes based on the

rectal resection specimen. The prefix "yp" is added as described for T status.

- Nx Regional lymph nodes cannot be assessed
- N0 No regional lymph node metastasis
- N1 Metastasis in 1-3 regional lymph nodes
- N2 Metastasis in 4 or more regional lymph nodes

11.5 Definition of Pathological Complete Response (pCR):

A pCR must include no gross or microscopic tumor identified anywhere within the surgical specimen. This must include no evidence of malignant cells in the primary tumor specimen **and** no lymph nodes that contain tumor.

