2.0 OBJECTIVES

2.1 Primary Objective

The primary objective of this study is to determine whether pre-operative short-course radiation therapy (SRT) and 6 cycles of TASOX offers condensed radiation and total neoadjuvant therapy for intermediate risk rectal cancer. The primary endpoint is to achieve a reduction in Neoadjuvant Response (NAR) score compared to historic controls.

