4.0 SCHEDULE OF TESTS

Test & procedures	≤ 28 days pre- registration	≤60 days prior to therapy	Prior to each cycle TASOX, - 3 days ¹	Pre-op visit after completion of cycle 6 TASOX, ie. ≤ 56 days after day 14, cycle 6 ^{8,10,12}	Post- Surgery 2-8 weeks post - op
History and physical	X		X	X	X
Pulse, BP and temperature	X		X	X	x
ECOG			X	X	X
Weight	Χ		X	X	X
Height	Χ				
Adverse Events ¹⁰			X	X	
Hematology ²	Χ		X	X	
Chemistry ³	Χ		X	X	
CEA	Χ		X	X	X
Pregnancy test ⁴	X		X— cycle #1 only		
Pathology confirmation of rectal adenoca.		$\mathbf{x} \leq 90 \text{ days}$			
Rectal exam and proctoscopy ⁵		X			
MRI of pelvis ^{6,8}		X		x ^{11,8}	
CT Chest or chest Xray ^{7,8}		X			
CT of abdomen with contrast ^{7,8}		X			
Documentation of post-operative complications- see					X
Section 6.4.					

1. Recommendations for timing of therapy:

- Radiation must commence within 3 weeks of study registration.
- Chemotherapy with TAS-102 must begin within 1-3 weeks after completion of radiation.

- Patients must have assessment at the time of progressive disease, study withdrawal, or removal.

2. Hematology includes hemoglobin, platelets and absolute neutrophil count (ANC).

3. Chemistry includes SGOT (AST), SGPT (ALT), total bilirubin, creatinine.

4. Urine or serum pregnancy test per institutional standard required for females of childbearing potential \leq 7 days of registration.

5. Rectal exam and proctoscopy are ideally to be performed by the primary surgeon. Proctoscopy should be performed \leq 90 days prior to registration or after registration but before the start of treatment. Proctoscopy may be accomplished using rigid proctoscopy or as part of a flexible sigmoidoscopy or colonoscopy.

6. Pelvic MRI Scan, with or without contrast per treating investigator/institutional standards, is to be performed within 60 days prior to treatment start. Use same imaging modality throughout the study.

7. A PET/CT scan may be performed in lieu of a CT scan with contrast, but a CT scan is preferred.

8. Scans do not have to be performed at the trial site; they can be performed at other locations as long as images are available for review. Scan is to be performed within </= 60 days prior to registration. Contrast is preferred but not required for the CT of the chest. Contrast is required for the CT of the abdomen.

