9. Recommendation: Surgery should be performed within 10 weeks AFTER the 6th cycle of neoadjuvant TASOX, and restaging investigations should be obtained within 8 weeks (56 days) AFTER day #14, cycle 6.

10. Adverse Events form to be completed at the start of radiation therapy.

11. Pelvic MRI should be booked within 56 days of completion of cycle #6 of TASOX, i.e. within 1-56 days AFTER day #14, cycle 6.

12. Patients that achieve a complete or near complete Clinical Response (cCR or ncCR) may choose to pursue a course of watch and wait with agreement of their treating surgeon. A thorough discussion is recommended with their surgeon concerning the risks and benefits of watch and wait and both they and their physician agree with the intended approach. Patients that pursue a course of watch and wait remain evaluable on study and will be classified as having a ypT0N0 response for the purposes of the NAR score if they do not proceed to TME surgery within 24 months of completing cycle 6, day 14.

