14.2 Sample Size

In table 2, the NAR scores of comparable patients enrolled in the phase III R04 study (27) and treated with long-course chemoradiation are presented (personal communications [name]). Patients with cT3N0 tumors and similar in stage to those to be enrolled in the proposed concept achieved a NAR score of 14.59 (SD 13.41). Prospective data suggests a 5.8 reduction in NAR score would be a clinically significant improvement in long terms outcomes. (15) For declared target 5.8 NAR reduction from 14.59 to 8.79 a sample size of 24 patients would be required, one-sided alpha=0.1 and beta=0.2 (Power 80.2%). Assuming an ineligibility rate of 10%, the final sample size is **27**.

Patients who pursue a course of watch and wait remain evaluable on study and will be classified as having a ypT0N0 response for the purposes of the NAR score if they do not proceed to TME surgery within 24 months of cycle 6 day 14.

R04 similar subgroup	Inclusion	Preoperative Therapy	Ν	ypT0N0 Rate	NAR Score
	cT1-3 cN any	LRT 50.4/25 plus Fluorouracil	631	18.4%	15.77 SD 14.17
	cT3 Non-Low	"	402	18.4%	16.05 SD 14.32
	cT3 cN0 Non-Low	"	293	20.2%	14.59 SD 13.41

Table 12. pCR and NAR scores in R04 patients.

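### Unoperated watch-and-wait patients get the best NAR category, while patients who miss TME through progression, unresectability or death have no scoring rule, which tilts the primary mean towards success

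*Combined protocol and SAP*

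**What the plan says.** The primary endpoint is a lower NAR score than in historical controls: "The primary endpoint is to achieve a reduction in Neoadjuvant Response (NAR) score compared to historic controls" (Section 2.1). The score needs pT and pN, and Section 11.4 says where they come from: "Derivation of the Neoadjuvant response (NAR) score requires pathologic staging information from the TME resection specimen".

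One exception is written down. Under note 12 of Section 4.0, "Patients that achieve a complete or near complete Clinical Response (cCR or ncCR) may choose to pursue a course of watch and wait". Section 14.2 then says: "Patients who pursue a course of watch and wait remain evaluable on study and will be classified as having a ypT0N0 response", on the condition "if they do not proceed to TME surgery within 24 months of cycle 6 day 14". Section 6.4 repeats the rule.

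The plan recognises that some patients may not reach surgery as intended. The restaging MRI is there for this purpose: "Repeat non-contrast pelvic MRI to rule out progressive disease and ensure surgical resectability" (Section 11.1). Section 4.0 adds: "Patients must have assessment at the time of progressive disease, study withdrawal, or removal". Neither passage gives the finding a consequence for the NAR score.

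The only allowance in the sample size is for ineligibility: "Assuming an ineligibility rate of 10%, the final sample size is" 27 (Section 14.2). Section 14 names no analysis set, no imputation or failure score, and no sensitivity analysis for patients without TME.

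**The concern.** Two kinds of patient may have no specimen, and the plan scores only one of them. A good responder who avoids surgery receives ypT0N0, the lowest NAR possible for any cT. A patient who progresses, becomes unresectable or dies before TME has no pT or pN and no substitute value. The natural reading is that this patient is left out of the mean.

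The favourable rule is also wide. It covers near-complete responders, and its only test is whether TME took place within 24 months. A watch-and-wait patient who regrows, progresses or dies without TME in that time still counts as ypT0N0.

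Whether a score is missing therefore depends on outcome. In a single-arm trial of about 24 patients judged against a fixed benchmark, one or two such patients can change the conclusion. If the rule is left open, it will be chosen after the outcomes are known.

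**Working it through.** **Inputs from the documents.** NAR = [5pN − 3(cT − pT) + 12]² / 9.61 (Section 1.3, Figure 1). Null mean 14.59 and SD 13.41 (Table 12, cT3 cN0 non-low). Reduction 5.8 to 8.79, one-sided alpha 0.10, n = 24, total 27 (Section 14.2).

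**Assumptions not in the documents.** The number of patients without TME, the scores they would have had, that 14.59 is an all-patient mean, and that the SD stays at 13.41.

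**1. The plan's own figure.** One-sample normal formula: n = [13.41 × (1.2816 + 0.8416) / 5.8]² = 24.10. Power at n = 24 is Φ(5.8 × √24 / 13.41 − 1.2816) = 79.9% (z), or 78.8% (t), against the stated 80.2%. Inflation: 24 / 0.9 = 26.7, so 27. The sample size reproduces; the problem lies in the scoring rule.

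**2. Scores for a cT3 tumour.**
- ypT0N0: 3² / 9.61 = 0.94
- ypT2N0: 9² / 9.61 = 8.43
- ypT3N0: 12² / 9.61 = 14.98
- ypT3N1: 17² / 9.61 = 30.07
- ypT3N2: 22² / 9.61 = 50.36

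**3. Leaving out k of 24 patients when the true all-patient mean is the null.** With would-be score v:
- mean of the rest = (24 × 14.59 − k × v) / (24 − k)
- type I error = Φ(−1.2816 + shift / (13.41 / √(24 − k))), where shift is 14.59 minus that mean

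| Omitted | v = 14.98 | v = 30.07 | v = 50.36 |
|---|---|---|---|
| 1 | 14.57; 10.1% | 13.92; 14.9% | 13.03; 23.4% |
| 2 | 14.55; 10.2% | 13.18; 21.5% | 11.34; 44.3% |
| 3 | 14.53; 10.3% | 12.38; 29.9% | 9.48; 67.9% |

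Each cell shows the mean of the scored patients and the one-sided type I error; the nominal error is 10%.

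Example, k = 2 and v = 30.07: (350.16 − 60.14) / 22 = 13.18. The shift is 1.41 and the standard error 13.41 / √22 = 2.86, so the error is Φ(−0.79) = 21.5%.

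**4. The watch-and-wait coding.** If two of 24 are coded 0.94 when their true category is ypT2N0 (8.43), the mean falls to 14.59 − 2 × (8.43 − 0.94) / 24 = 13.97 and the error is 14.6%. One unoperated regrowth coded 0.94 and not 50.36 lowers the mean by (50.36 − 0.94) / 24 = 2.06.

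**5. Power with fewer scores.** With 22 evaluable, power is 77.3% (z) or 76.0% (t). Compared like for like, that is down from 79.9% or 78.8%. Reaching 22 from 27 means losing five patients to ineligibility and missing scores together.

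**The case against.** **The plan does not say that failures are excluded.** This is correct. No analysis set is defined, and a reader who infers a stated exclusion goes further than the text. What stands is that Section 11.4 leaves no way to score these patients and no other section supplies one.

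**Failures should be few.** Section 3 excludes T4, N2 and threatened-margin tumours and requires sphincter-sparing resectability at entry. The MRI is a check and does not predict that progression will be found. This limits the likely count, but one or two patients are enough to matter at n = 24.

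**Toxicity is not a route to a missing score by itself.** A reader might infer it from the discontinuation rules in Section 8. Those rules stop study drug, and none cancels surgery, so a patient who stops TASOX early can still have TME and a score.

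**Regrowth can be scored.** This is true if TME takes place within the 24 months. It does not help with regrowth, progression or death without TME.

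**The benchmark may have the same gap.** Section 14.2 does not say whether the R04 means include unresected patients. If they used resected patients only, part or all of the omission bias cancels, and an all-patient mean would be the less like-for-like comparison. This is the strongest objection, and the documents cannot settle it. They describe no watch-and-wait coding for R04, so nothing shows that this part cancels.

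**Failures would still be seen.** Adverse events and surgical complications are the secondary objective, and assessment at progression is required. The concern is therefore limited to the primary mean; it is not that failures go unrecorded.

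**Conclusion.** The concern holds as an asymmetric scoring rule. The favourable route to having no specimen is given the best category; the unfavourable routes of progression, unresectability and death have no score and, by implication, leave the mean. The direction is towards success.

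The size is conditional. With 14.59 taken as an all-patient mean and SD 13.41, omitting 1 to 3 of 24 leaves the error at about 10% if those patients would have scored near the benchmark (14.98). It rises to 15-30% at 30.07, and to about 44% for two patients at 50.36. A reader might take the higher figures as the trial's actual false-positive rate. The documents do not support that, because they give neither the number of failures nor their would-be scores, nor the R04 analysis set.

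Nor should 76-77% at 22 evaluable be set against the stated 80.2% as the power loss. Like for like, the loss is under three points. Bias is the main issue, with lost power secondary.

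The plan should be changed before outcomes are known, because the gap can affect the conclusion and is easy to close.

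**What to change.** In Section 14.2:

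- Define the primary analysis set as all eligible patients who start radiation.
- Pre-specify an unfavourable NAR for patients without TME because of progression, unresectability or death, for example pT = cT with pN = 2 (50.36 for cT3). The exact value is a choice; fixing it in advance is the essential step.
- Apply the same score, and not ypT0N0, to watch-and-wait patients with regrowth, progression or disease-related death without TME.
- State how patients without TME for other reasons (refusal, withdrawal, medical unfitness) are handled.
- Report both the all-patient mean and the resected-plus-watch-and-wait mean. Confirm the R04 analysis set and say which mean is like-for-like.
- List every patient without TME, with the reason.

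**Cost.** A change of wording and one further analysis. No patients need be added if the possible loss of power is accepted. At n = 24 the success boundary is 14.59 − 1.2816 × 13.41 / √24 = 11.08. If scored patients average the target 8.79, one failure at 50.36 gives (23 × 8.79 + 50.36) / 24 = 10.52, still a success, with power of about 58%. Two give (22 × 8.79 + 2 × 50.36) / 24 = 12.25, which misses the boundary, with power of about 33%. R04 may not have used such a scoring rule, which is why both means are needed.

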12.0 POST-OPERATIVE THERAPY

Recommendations for post-operative systemic therapy are not protocol specified and are according to recommendation of the investigator based clinical evidence and NCCN guidelines. Post-operative FOLFOX or 5-Fluorouracil plus Leucovorin/Capecitabine may be recommend taking into consideration clinical and pathologic stage and patient preference.

